OXPHOS/Glycolysis (OCR/ECAR; **Figure 3C**). These data demonstrate our ability to measure mTOR activation in small numbers of immune cells from children.

Hypothesis, Specific Aims, and Objectives

In this study, we hypothesize that compared to lean children, circulating CD4⁺T cells from obese children with elevated biomarkers of inflammation will have fewer T_{regs} and will exhibit increased mTOR-driven glycolysis. Metformin treatment will increase T_{regs} and shift the metabolic phenotypes of CD4⁺T cells towards AMPK-driven OXPHOS. We will test these hypotheses by executing the following Specific Aim:

Specific Aim 1. Compare the immune and metabolic phenotypes of circulating CD4⁺T cells between lean children and overweight/obese children.

Hypothesis: circulating CD4⁺T cells from obese children with elevated biomarkers of inflammation will have fewer T_{regs} and will exhibit increased mTOR activation and % glycolysis-derived ATP production as compared to CD4⁺T cells from lean children.

Specific Aim 2. Compare the immune and metabolic phenotypes of circulating CD4⁺T cells between T2D children before and after metformin.

Hypothesis: In obese T2D patients, metformin treatment will increase circulating T_{regs}, as well as AMPK activation and % OXPHOS-derived ATP production in CD4⁺ T cells.

Study Design and Procedures

This study consists of:

1. An observational cross sectional immune and metabolic analysis of several groups of children including lean, overweight/obese, and T2D.
2. A prospective immune and metabolic analysis of newly diagnosed children with T2D or insulin resistance who will be or were recently prescribed metformin as part of their clinical care.

Children with T2D or insulin resistance who will be or were recently prescribed metformin, will be asked to complete two study visits. If completed, the second visit will occur 6 months (+/- 2 weeks) after beginning metformin as part of their clinical care. All other children, will be asked to complete only the first visit.

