At the initial study visit eligible participants will be met by study staff at the designated study location. Participants will arrive after not taking seasonal allergy medication in the previous 72 hours and an overnight fast of no food or liquid after 12 am, except for water and medications the day of the visit. The study visit may include collection of anthropometric measurements, tanner stage assessment, physical activity questionnaire, depression scale, body composition by bioelectrical impedance, blood, stool, and urine collection. Attempts to repeat anthropometric measurements, and body composition by bioelectrical impedance, will occur if a reading is not given the first time or if the child is unable to comply during the first measurement. For optional sample collection (i.e., urine and stool), the parent and participant will not have to stay at the research location for the entire visit in order for the samples to be obtained. Instructions will be given to the parents for collection of samples if the parent and child decide not to remain at the research location for the entire visit.

If a procedure(s) (see below) is not successfully completed, the parent and, if warranted, the participant may be asked to return to the study site for an additional visit to re-attempt the procedure. The decision to ask the parent/participant, to return for another attempt will be made by the principal investigator. When a decision is made to re-attempt the procedure, study staff will contact the parent and explain what procedure they would like to re-attempt and if the parent is willing, schedule the visit. If a blood draw will be re-attempted, the parent will be re-advised that if the parent wishes their child to complete the procedure, the child will need to not have taken seasonal allergy medication in the previous 72 hours and be fasting including no food or liquid after 12 am, except for water and medications the day of the visit. The study visit will be conducted in the same manner as the initial visit, with only the desired procedure(s) being re-attempted.

Title: Immunometabolism in Pediatric Obesity

PI: [name].

The collection of urine and stool samples is optional, and these samples may not be collected if the subject or parent does not want the sample(s) to be used for future research.

Study Procedures to be conducted at each visit:

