If agreed to, the second visit for children with T2D or insulin resistance who will be or were recently prescribed metformin will occur 6 months (+/- 2 weeks) after beginning metformin as part of their clinical care. This additional study visit is optional as we do not want to discourage potential enrollment due to the possibility of multiple visits or lengthy visits. We anticipate 50% of the participants in this group will decline a 2nd study visit with a goal of 10 subjects completing a 2nd visit at 6 months (\pm 2 weeks). The second study visit will include the same procedures as the first study visit. In addition, participants/parents will be asked to verify their compliance with metformin by bringing their medication to the visit to show study staff and asking the parent/participant to report their compliance. As done for the first study visit, if a procedure(s) is not successfully completed, the parent and, if warranted, the participant may be asked to return to the study site for an additional visit to re-attempt the procedure. The decision to re-attempt the procedure(s) will be made by the principal investigator and the same steps as described for the re-attempt of a procedure from the initial visit followed.

A participant/parent pair will be compensated for each study visit completed. For the first and, if applicable, second study visit, a \$50 gift card (or gift cards totaling \$50) will be provided to the study participants/parents after completion of the procedures to be completed at the research site (e.g., anthropometric measurements, Tanner Stage Assessment, physical activity questionnaire, depression scale, body composition, and blood collection). Parents/participants with T2D or insulin resistance who are prescribed metformin therapy will be asked to complete two study visits and will be paid up to \$100.00 in gift cards (\$50.00 in gift cards at the first study visit completed and \$50.00 in gift cards at the second visit completed). Other parents/participants will be asked to complete one visit and will be paid up to \$50 in gift cards for this completed visit. Those participants/parents who are asked to return to re-attempt procedure(s) not successfully completed at a study visit (initial or second) will be given a \$25 gift card after re-attempting

Title: Immunometabolism in Pediatric Obesity

PI: [name].

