There is the potential risk of loss of confidentiality to study participants. Measures to protect the confidentiality of study participants will be implemented by applying the appropriate steps to secure the collected data as described in the Data Handling and Recordkeeping section below. There is a small risk that participants will encounter bruising and/or infection after having blood taken, however, the use of well-established blood taking techniques, and sterile procedures, by trained phlebotomists or nurses, will ensure the risk is minimal. Also, numbing cream, numbing spray, and/or a pain relieving device (Buzzy) may be used to minimize the pain associated with the blood draw. There is the risk that researchers could develop ways in the future to link genetic information back to the subjects even though the stored samples do not include any personal identifiers, except for the assigned unique study code, study visit number, and the study acronym. Any adverse effects or unanticipated problems will be reported to the study PI, the IRB, and the study sponsor in accordance with IRB Policy 10.2. There will be no direct benefits to the study participants; however, knowledge gained from the study could potentially benefit patients in the future.

Title: Immunometabolism in Pediatric Obesity

PI: [name].

Data Handling and Recordkeeping

The Principal Investigator will carefully monitor study procedures to protect the safety of research subjects, the quality of the data and the integrity of the study. All study subject material will be assigned a unique identifying code or number. The electronic key to the code will be kept in a secure, access-restricted, pass-code required, location created specifically for the study. Only the PI and research personnel will have access to the code and information that identifies the subject in this study.

The PI and research study personnel will complete and maintain appropriate CITI training. Source documents and CRFs will be stored in a locked location. Documents will be archived according to UAMS/ACH/ACRI policies regarding destruction of research records.

Data will be entered into a research database. Access to the study database(s) is password protected and will be limited to study personnel and regulatory authorities.

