At the time of collection, samples will be kept on ice or refrigerated (with the exception of stool which will be kept in a freezer) in the pediatric clinical research unit or in [name] laboratory (Rm 4015 of ACRI) until they can be transported to the research or hospital laboratory.

For testing to be completed by the Arkansas Children's hospital laboratory (e.g., HbA1c), sample(s) will be labeled with the participant's medical label generated through EPIC which includes the participant's name, date of birth, gender, and medical record number. This sample will be provided to the hospital laboratory where they will complete the testing, storage, and disposal of the sample per their standard operating procedures. Results will be reported through the participant's medical record.

For testing to be completed by [name] laboratory, samples will be kept at -80°C once the initial processing and analyses have taken place. These samples will be stored in the Arkansas Children's Research Institute, Room R4017 Freezers 4017FT12 or R4017FT8 or R2108 Freezer R2108FT16. Cryopreserved samples may also be kept under liquid nitrogen in the Arkansas Children's Research Institute, Room R4017. These are monitored continuously for proper temperature and working condition. None of a subject's personal identifiers will be present on any biological sample, except the unique subject ID, study visit number, and the study acronym. The samples may be used until they are used up for research on pediatric nutrition or metabolism.

At any time if the subject decides that he/she does not want to participate anymore, that subject's data will be included as part of the planned analysis of study data. No more information will be collected after withdrawal, however all data and samples collected prior to withdrawal will still be used.

Information pertaining to this study will be made publically available through the ClinicalTrials.gov website.

Data Analysis

Title: Immunometabolism in Pediatric Obesity

PI: [name].

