Prior to any analyses, endpoints data for each group will be closely inspected for the potential presence of unusual values; effort will be made to conserve all data. Analyses will be carried out in SAS 9.4 (SAS Institute, Cary NC) at the 5% significance level; point and 95% interval estimates will be obtained for relevant metabolic group comparisons. Parametric techniques will be first choice and nonparametric equivalents if assumptions are not met. Special attention will be paid to unequal variances.

The study planned four groups of children: lean, healthy obese/overweight, insulin-resistant obese/overweight, and overweight/obese with T2D. Primary comparison of interest are these three: the average of insulin-resistant and T2D obese children compared to (i) lean children and (ii) healthy obese children; and (iii) lean children compared to healthy obese children. Outcomes important to this aim are proportions of T_{reg} cells among circulating CD4 $^{+}$ T cells and CD4 $^{+}$ T glycoATP and mitoATP production. Initially, we will use a one-factor ANOVA to analyze these outcomes (possibly with suitable transformations). Comparisons of interest will then be made with 0.05 significance level *t*-tests conducted within the ANOVA framework.

The requested sample sizes will provide about 0.80 power for detecting differences in means of size 0.8 SD for comparisons (i) and (ii) and size 0.9 SD for comparison (iii), where SD is the within-group standard deviation (a.k.a., root mean square error from the ANOVA). For proportions of T_{reg} cells – a primary outcome of interest, an estimate of the SD is 2.3 percentage points (ref Table 1 of Arismendi et al.⁴²). So, if the means differ by at least 1.85 percentage points in comparisons (i) & (ii) and by 2.10 percentage points for comparison (iii), we will be able to detect these differences with a reasonably high probability (0.80 or higher).

Ethical Considerations

This study will be conducted in accordance with all applicable government regulations and University of Arkansas for Medical Sciences research policies and procedures. This protocol and any amendments will be submitted and approved by the UAMS Institutional Review Board (IRB) to conduct the study.

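### The plan does not mask assay readers or the review of unusual values to group or visit, and the sample label identifies the roughly 10 post-metformin samples of Aim 2

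*Combined protocol and SAP*

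**What the plan says.** Four provisions of the combined protocol and SAP bear on this point.

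- **Labels (Data Handling and Recordkeeping).** Samples for the research laboratory carry no personal identifiers "except the unique subject ID, study visit number, and the study acronym". Risks and Benefits and Ethical Considerations describe the same label. It contains no group code.
- **Who attends twice (Study Design and Procedures).** "Children with T2D or insulin resistance who will be or were recently prescribed metformin, will be asked to complete two study visits". For the rest: "All other children, will be asked to complete only the first visit". The second visit is optional. Half of those eligible are expected to decline, "with a goal of 10 subjects completing a 2nd visit at 6 months".
- **The key (Data Handling and Recordkeeping).** It is held in a restricted, passcode-protected location. "Only the PI and research personnel will have access to the code and information that identifies the subject in this study". Assay readers are not excepted.
- **Unusual values (Data Analysis).** Before any analysis, "endpoints data for each group will be closely inspected for the potential presence of unusual values". The same sentence states an intention to retain all data. There is no rule for calling a value unusual or for excluding it.

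The blood collection procedures name flow cytometry for immunophenotyping, the Seahorse analyzer for bioenergetics (on fresh or cryopreserved cells), and immunoassays or western blot for pathway activation. They give no gating rule and do not mention masking.

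**The concern.** The hypotheses have a direction: fewer regulatory T cells and more glycolysis in obese children with inflammation, and more regulatory T cells after metformin. Where a gate is placed, which run is kept and whether a value is set aside leave room for judgement. If the person deciding knows the group or visit, those choices can drift towards the expected result. An ANOVA or t-test cannot detect or remove such drift afterwards, because it enters the data as a difference in means.

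Aim 2 is the more exposed part. It is a before/after comparison with no untreated arm and about 10 pairs, and the label itself shows which sample is the later one.

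**Working it through.** The point turns on what each provision reveals and to whom. The arithmetic is limited to counts and one check of the plan's power statement.

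**1. The plan's own figures.** Data Analysis states about 0.80 power for 0.8 SD in comparisons (i) and (ii) and for 0.9 SD in (iii). Study Population gives about 20 children in each of four groups; a two-sided 0.05 test is assumed.
- (i) and (ii), average of two groups against one: variance factor (1/20 + 1/20)/4 + 1/20 = 0.075. Noncentrality 0.8/√0.075 = 2.92. Power with 76 df = 0.82.
- (iii), one group against one: variance factor 1/20 + 1/20 = 0.10. Noncentrality 0.9/√0.10 = 2.85. Power with 76 df = 0.80.

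The statement reproduces. Masking changes neither sample size nor power, so no figure in the plan is at fault.

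**2. What the visit number reveals.**
- First visit: 20 + 20 + 20 + 20 = about 80 completers, all with the same visit number. The label does not separate lean, healthy obese, insulin-resistant and T2D children.
- Second visit: half of about 20 = about 10 samples, all from children prescribed metformin.
- The label is therefore informative for about 10 of 80 + 10 = 90 samples, or 11%. Those 10 are the whole post-treatment side of Aim 2.

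**3. Whether another child could hold a visit-2 sample.** After an incomplete procedure, "the participant may be asked to return to the study site for an additional visit to re-attempt the procedure". This can happen in any group, and the numbering of such visits is not stated. The compensation paragraph lists first, second and re-attempt visits separately, which suggests that a re-attempt is not numbered as visit 2. The inference from visit 2 to post-metformin is strong but not absolute.

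**4. What bears on comparisons (i) to (iii).**

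| Provision | Stage affected | What it permits |
|---|---|---|
| Key open to research personnel | Gating and assay read-out | A reader could learn group; nothing shows that readers do |
| Inspection of unusual values by group | After read-out | Exclusions could be decided by group, with no rule |

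The second provision concerns exclusion, not how a value is read.

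**5. What the plan says about masking.** No section masks readers or the reviewer of unusual values, and none says that they know group or visit.

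**6. Size of any bias.** The documents give no reader shift, between-reader variation or exclusion rate. They also give no detectable difference for Aim 2. No size can be derived.

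**The case against.** The strongest reply is that the documents are silent, and silence is not evidence of unmasked reading. A reader might infer that the regulatory T cell and ATP values are read with group known. The documents do not support that: samples are coded, the label carries no group, the key is restricted, and permission to access a key does not show that it is consulted during gating. Insulin-resistant status is to be assigned from insulin sensitivity, so for much of comparison (ii) the subgroup may not be known when fresh cells are read. This stands.

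A reader might also set an assumed gating shift against the 1.85-point difference given for comparisons (i) and (ii) and report the ratio as the harm. That only rescales an assumption, and it uses comparisons in which the visit label reveals nothing. Such a figure should not be used.

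The replicate-well averaging under Preliminary Data comes from a different assay in mixed blood cells from an autism study. It does not show how wells will be chosen here.

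On unusual values, the plan intends to keep all data, which limits the harm. Inspection within groups is also a natural check before an ANOVA with attention to unequal variances, and it could be done under coded group labels. Reviewing values pooled over groups would be worse, because genuine values from a shifted group could look like outliers.

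These points do not answer the visit-2 label, the key access without an exception for readers, or the absence of an exclusion rule.

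**Conclusion.** The concern holds as an omission that is cheap to repair. Followed as written, the plan shows the reader which samples are post-metformin in a comparison of about 10 pairs. It also leaves exclusions to be decided group by group without a rule. For comparisons (i) to (iii) the exposure is weaker: the label is uninformative, and the risk lies in possible key access and by-group inspection.

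No magnitude is claimed. The conclusion assumes that the second-visit goal of about 10 is met, that re-attempts are not numbered as visit 2, and that gating and exclusion involve some judgement, since the plan fixes no rule for either. It does not assume that any reader is in fact unmasked, and it does not question the sample size or the stated power.

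**What to change.** 1. **Recode before read-out.** Before flow gating and before Seahorse and immunoassay read-out, existing study staff rename the files and lysates with a random code that carries neither subject ID nor visit number. Assay readers have no access to the list or to the study key.
2. **Fix the gating.** Readers apply one gating template, set in advance, to all coded files.
3. **Amend Data Analysis.** Inspect unusual values within groups under masked group and visit codes, not pooled over groups. Decide, record and lock any exclusion before the codes are linked to group and visit. Keep the intention to retain all data.
4. **State the masking.** Add one sentence to Data Handling and Recordkeeping saying who is masked, to what, and until when.

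The cost is a recoding list, some file handling and a short amendment. It needs no extra visits, samples or staff, and power is unchanged. Same-day processing of fresh cells cannot be fully masked; the protection applies to gating, read-out and exclusion decisions.

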Obesity is strongly linked to systemic inflammation with increased circulating pro-inflammatory cytokines and adipokines and elevated C-reactive protein (CRP) reported in obese children as young as age three¹⁰⁻¹⁵. Examining NHANES data from over sixteen thousand children, Skinner et al¹⁵ found that prevalence of C-reactive protein (CRP) levels >1mg/L was greater in very obese children beginning at age 3 and continued through adolescence, with greater than 80% of very obese adolescents having CRP >1mg/L as compared to 18% of lean adolescents. While the dataset did not permit controlling for pubertal age, similar results were found even when very narrow age groups were compared. In a smaller study of children ages 7-14 years, Codoner-Franch et al¹⁶ classified obese children as metabolically healthy or at risk based on well-defined criteria, and they reported CRP, Tumor necrosis factor α (TNF α) and Interleukin (IL) 6 were all increased in obese children with or without metabolic risk factors, suggesting that inflammation may appear early in obesity before metabolic alterations. Inflammation is considered pivotal to the development of obesity-related metabolic disorders including insulin resistance, T2D¹⁷⁻¹⁹ and cardiovascular dysfunction^{20, 21}. Modulation of inflammation in obese children provides a putative “target” for therapeutic intervention.

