Suppression of inflammation is a function of regulatory T cells (T_{regs}), a subset of CD4 $^{+}$ T cells also responsible for maintenance of peripheral tolerance and suppression of antigen-specific immune responses. However, decreased circulating T_{regs} have been reported in T2D²² and obese^{23, 24} adults. Wagner et al²⁴ found that reduced T_{regs} predicted a CRP level greater than 3mg/L and may therefore predict those at increased cardiovascular risk; however, a separate group reported no differences in T_{regs} between severely obese subjects with and without hypertension²³. As in humans, T_{regs} are reduced in several mouse models of obesity, especially VAT-resident T_{regs} , with a concomitant increase in VAT-resident T effector cells^{25, 26}. A critical role for T_{regs} in the development of insulin resistance has been demonstrated in these models. Winer et al²⁵ elegantly demonstrated that adoptive transfer of CD4 $^{+}$ T cells into lymphocyte deficient DIO Rag1 $^{-/-}$ mice reduced weight gain and improved glucose tolerance. *In situ* induction of T_{regs} in HFD obese wild-type mice with anti-CD3 antibody also resulted in improved glucose tolerance and insulin sensitivity, which persisted for months despite being maintained on

HFD. Feuerer et al²⁶ demonstrated that depletion of adipose T_{regs} in transgenic mice expressing the diphtheria toxin receptor in T_{regs} induces insulin resistance and increased inflammatory mediators in the adipose tissue. Conversely, *in situ* induction of T_{regs} with recombinant IL-2 and IL-2 monoclonal antibody increased VAT-resident T_{regs} and improved glucose tolerance in HFD obese mice. Findings from these two landmark studies have been replicated in other mouse models of obesity^{27, 28}. Targeting T_{regs} may modulate inflammation in obesity; however, whether T_{regs} are altered in early stages in obesity (e.g. overweight/obese children) remains unknown. In this study, we will fill an important research gap by testing whether obese children exhibit decreased circulating T_{regs} as compared to healthy lean children.

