Figure 2: The ATP production rate assay demonstrates increased % glycolysis-derived ATP production in PBMC from T2D children. Oxygen consumption rate (OCR) (A) and Proton Efflux Rate (PER) (B) are plotted over time in PBMCs from lean, obese (OB) and type 2 diabetic (T2D) children. Injections of Oligomycin (oligo) and Antimycin A (AMA) and Rotenone (ROT) are indicated. (C) Glycolytic ATP production rate (glycoATP) and mitochondrial ATP production rate (mitoATP) are calculated from OCR and PER. (D) % glycolysis and % OXPHOS-derived ATP production are calculated. * $p=0.032$

Methods: Freshly isolated PBMC from lean ($n=8$), obese (OB; $n=11$), and treatment-naive type 2 diabetic (T2D; $n=2$) children were plated at 2.5×10^6 cells/well in RPMI 1640 with 1mM HEPES, 2mM glutamine, 1mM pyruvate and 11mM glucose on poly-D-lysine coated XF96 plates. Plates were centrifuged at 100xg with no brake to adhere cells to well bottoms. After a 30 min incubation in a 37°C non-CO₂ incubator, cells were assayed in a Seahorse XF96.

note regarding this data: 1) these data are from PBMC, a mixed population of cells including monocytes and lymphocytes of various subtypes rather than purified CD4⁺ T cells as proposed in this study; 2) the obese subjects have not been classified as metabolically healthy or unhealthy; 3) the age of the T2D subjects is greater (16.5±0.1 years; mean±SD) than the other groups (lean: 6.8±1.1 years; obese: 7.9±1.4 years). In the studies proposed herein, we will match groups on age and subgroup obese subjects as metabolically healthy and unhealthy based on insulin sensitivity. Further, after measuring high sensitivity CRP (hsCRP), we will compare subjects with hsCRP values in the top quartile to the other groups to determine whether the % glycolysis is higher in CD4⁺T cells from those obese subjects with inflammation.

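### Aim 1's hypothesis concerns obese children with raised inflammatory markers, but no planned analysis tests it for Treg proportion or mTOR activation, and mTOR is missing from the Data Analysis outcomes

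*Combined protocol and SAP*

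**What the plan says.** Under Hypothesis, Specific Aims, and Objectives, the Aim 1 hypothesis has two parts. On Tregs, it says that "obese children with elevated biomarkers of inflammation will have fewer" of these cells than lean children. On metabolism, it says that their CD4+ T cells "will exhibit increased mTOR activation and % glycolysis-derived ATP production as compared to" those of lean children. It therefore names a population defined by inflammation and three outcomes.

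Data Analysis defines four groups by weight and metabolic status: lean, healthy overweight/obese, insulin-resistant overweight/obese, and overweight/obese with T2D. Comparisons (i) and (ii) are "the average of insulin-resistant and T2D obese children compared to (i) lean children and (ii) healthy obese children", and comparison (iii) is lean against healthy obese. The outcome sentence begins "Outcomes important to this aim are proportions of" Treg cells and goes on to the glycolytic and mitochondrial ATP production rates. Neither an inflammatory marker nor mTOR appears in the section.

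The only comparison based on inflammation is at the end of the Figure 2 discussion in Preliminary Data: once hsCRP is measured, "we will compare subjects with hsCRP values in the top quartile to the other groups to determine whether the % glycolysis is higher". It is aimed at CD4+ T cell samples "from those obese subjects with inflammation".

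The measurements themselves are planned. The background says that AMPK and mTOR activation will be measured in isolated CD4+ T cells, and the blood collection procedure covers CRP and the metabolic control pathway analytes.

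**The concern.** The hypothesis selects children by inflammation, whereas the analysis selects them by insulin resistance and diabetes. If the plan is followed as written, Treg proportion, which Data Analysis treats as a primary outcome, is never compared by inflammatory status. mTOR activation has no planned Aim 1 analysis of any kind. A null result for comparison (i) would not refute the hypothesis, and a positive one would not link the difference to inflammation.

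The protocol's background also cautions against reading metabolic group as inflammation. In the study of children aged 7 to 14 that it cites, CRP, TNF-alpha and IL-6 "were all increased in obese children with or without metabolic risk factors, suggesting that inflammation may appear early in obesity before metabolic alterations". The choices left open in the single hsCRP sentence could also be settled after the data have been seen.

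**Working it through.** **1. Hypothesis against plan.**

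| Hypothesised outcome (Aim 1) | Listed in Data Analysis | Compared by metabolic group | Compared by inflammation |
|---|---|---|---|
| Treg proportion | Yes | Yes, (i) to (iii) | Nowhere |
| mTOR activation | No | No | Nowhere |
| % glycolysis-derived ATP | Through the two ATP rates | Through the two ATP rates | One sentence, Preliminary Data |

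None of the three outcomes has an inflammation comparison in Data Analysis. One of the three has one elsewhere in the protocol.

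**2. The plan's own power.** Inputs are about 20 children in each of four groups (Study Population: 20 lean, 40 overweight/obese of whom about 20 insulin resistant, 20 T2D), the 0.05 level, and differences of 0.8 and 0.9 SD (Data Analysis). Sidedness is not stated; I assume two-sided tests. Error df = 80 − 4 = 76. The noncentrality is d / √(1/n₁ + 1/n₂), and power comes from the noncentral t distribution.

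- (i) and (ii), 40 against 20: 0.8 / √(1/40 + 1/20) = 0.8 / 0.274 = 2.92; power 0.82.
- (iii), 20 against 20: 0.9 / √(1/20 + 1/20) = 0.9 / 0.316 = 2.85; power 0.80.
- In Treg points with the plan's SD of 2.3: 1.85 / 2.3 = 0.804 SD gives 0.83, and 2.10 / 2.3 = 0.913 SD gives 0.81.

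The stated power of about 0.80 holds for the comparisons that it describes. No power is stated for an inflammation-defined comparison.

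**3. What the hsCRP sentence leaves open.** It fixes the marker, the cut (top quartile) and the outcome. It does not say which children the quartile is taken over, whether T2D children count, or what happens to a lean child above the cut. The group sizes below are assumptions, one for each reading. Each is set against 20 lean children, two-sided 0.05, two-sample df, unadjusted.

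| Quartile taken over | High-hsCRP n | Power at 0.8 SD | Difference detectable with 80% power |
|---|---|---|---|
| 40 overweight/obese without T2D | 10 | 0.51 | 1.124 SD = 2.59 Treg points |
| 60 overweight/obese including T2D | 15 | 0.62 | 0.986 SD = 2.27 points |
| All 80, if none of the top 20 is lean | 20 | 0.69 | 0.909 SD = 2.09 points |

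For n = 15 the steps are: 60 / 4 = 15; 0.8 / √(1/15 + 1/20) = 0.8 / 0.342 = 2.34; df 33; power 0.62. The 95% CI half-width for Treg proportion is about 2.03 × 2.3 × 0.342 = 1.6 percentage points.

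**4. Whether metabolic group can stand in for inflammation.** Preliminary Data gives a reason for metabolic grouping: the higher % glycolysis in T2D children is read as a sign of more pro-inflammatory cells and fewer Tregs. The background, however, reports raised markers with or without metabolic risk factors. On that evidence the healthy obese group may contain inflamed children, and comparison (i) leaves those children out. Metabolic group is therefore an imperfect proxy for inflammation.

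**The case against.** The best defence is that the aim itself, as distinct from its hypothesis, is analysed. Specific Aim 1 compares lean with overweight/obese children, and the background describes the study as "testing whether obese children exhibit decreased circulating" Tregs relative to lean children, without an inflammation qualifier. Comparisons (i) and (iii) serve that purpose. This stands. A reader might infer that Aim 1 goes untested, or that the primary comparisons are invalid or underpowered; the documents support neither reading.

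A reader might also infer that the plan ignores inflammation. It does not. The hsCRP sentence describes an analysis intended for this study, and the general rules in Data Analysis (5% level, parametric methods first, attention to unequal variances) partly settle how it would be tested. What remains open is narrower: the set of children that forms the quartile, and the handling of T2D and lean children.

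A third objection is that a high-hsCRP versus lean comparison has its own limits. Those groups differ in weight as well as inflammation. A group formed by hsCRP does not inherit the age, sex and ethnicity balance sought for the recruitment groups, and the Tanner procedure says that puberty must be accounted for. At a given difference the comparison is also less powerful than (i): 0.62 against 0.82 at 0.8 SD. All of this stands. It is why the fix adjusts the comparison and adds a slope within overweight/obese children. The reason to add the comparison is that it asks the hypothesised question, not that it is more sensitive.

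Finally, it is tempting to put a figure on the power lost by using metabolic group as a proxy. The documents do not give the share of inflamed children in these groups. The survey figures in the background (over 80% of very obese and 18% of lean adolescents with CRP above 1 mg/L) describe other populations. I therefore give no such figure.

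**Conclusion.** The point holds as a mismatch between hypothesis and analysis. Two of the three hypothesised outcomes, Treg proportion and mTOR activation, have no planned test against inflammation. mTOR activation is absent from the Aim 1 outcome list altogether. The third outcome, % glycolysis, has an hsCRP comparison that sits outside Data Analysis and is incompletely defined.

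This conclusion rests on the text alone and does not depend on the group-size assumptions. Those assumptions bear only on what an added analysis could deliver, which is modest. The change should be made, but its absence does not undermine the primary comparisons.

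**What to change.** In Data Analysis, as secondary analyses reported as estimates with 95% confidence intervals:

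1. Add mTOR activation to the Aim 1 outcomes for the existing comparisons (i) to (iii).
2. For Treg proportion, % glycolysis and mTOR activation, compare overweight/obese children (T2D included) above one hsCRP cut with lean children, adjusted for age, sex and Tanner stage. Fix the cut before outcome data are seen, for example the top quartile of all overweight/obese children, about 15 of 60. Place each child in one group only. This replaces the sentence in Preliminary Data.
3. Because step 2 cannot separate inflammation from weight, also regress each outcome on continuous log(hsCRP) among overweight/obese children, adjusted for age, sex and Tanner stage, with and without metabolic group. Rest any statement about inflammation on this slope.

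Alternatively, reword the Aim 1 hypothesis to match the metabolic comparisons, keep mTOR activation as an outcome, and label the hsCRP comparison exploratory. This gives up the inflammation claim.

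The cost is text only. CRP and the pathway analytes are already to be measured, so no new sample or visit is needed. Steps 2 and 3 add about six secondary tests (3 outcomes × 2 analyses), and step 1 adds mTOR to three existing comparisons. Power is modest: about 0.62 at 0.8 SD for an assumed 15 against 20 before adjustment.
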